Buprenorphine Induction and Stabilization: Participants will be inducted onto buprenorphine prior to beginning the buprenorphine taper. Induction may occur up to 3 weeks prior to admission to the CRU. Participants will be required to show evidence of opioid withdrawal (as per ratings on the COWS) and will receive incremental doses of buprenorphine throughout the day, up to a maximum of 16mg of buprenorphine on the induction day. The induction protocol will be conducted as clinically indicated, based upon medical team recommendations. To increase comfort during the induction, the medical team may administer the PRN concomitant medications that are approved for the taper protocol as well as clonidine. Participants may then be maintained on buprenorphine as an outpatient for up to 3 weeks before CRU admission. Briefly maintaining participants on buprenorphine will enable the study to retain participants between Screening and CRU admission, as the CRU has restricted access for protocols requiring weekend coverage. Participants who are maintained on buprenorphine as an outpatient will receive blister packages of sublingual buprenorphine for outpatient administration and may receive up to 24mg/day (beginning the day after induction) during this period. During the stabilization period between Screening and Admission, participants will be required to visit the clinic on a weekly basis to exchange blister packages. Participants may receive assistance (e.g., bus tokens) from the study to help facilitate transportation to the BPRU on those days. Any participant receiving >16 mg as an outpatient will be transitioned to 16mg on the CRU admission day. Participants who are inducted onto buprenorphine on the CRU admission day will follow an identical induction procedure and will only receive up to 16mg.

Clinical Research Unit (CRU): Following confirmation of eligibility, participants will be admitted onto a residential CRU that is located on the Bayview Medical Campus. Participants will reside on the CRU for up to 11 days (10 nights) and will be allowed to smoke cigarettes ad libitum in a designated smoking area during their stay. Female participants will provide a sample of blood upon admission that will be analyzed for levels of progesterone and estrogen.

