Brief Sleep Hygiene Education: During stabilization, staff will conduct a brief educational session with participants to provide information regarding appropriate sleep hygiene (Doshi et al., 2017). This session will ensure all participants have the same understanding of healthy sleep behaviors before the taper begins, to minimize the impact that differences in sleep hygiene has, and better isolate the impact of SUVO on study outcomes.

Overdose Education: During the stabilization period, participants will also complete a brief opioid overdose prevention computerized education session (developed by Co-I Dunn under NIDA R21DA035327).

Randomization to Group: Participants will be stratified into experimental group based on (a) baseline Pittsburgh Sleep Quality Index (PSQI) (<5/≥5), (b) peak SOWS ratings during buprenorphine induction (≤10/>10), (c) buprenorphine stabilization dose (<16mg/16mg), and (d) sex (M/F). Randomization will occur via a minimization procedure to balance the distribution of these characteristics

across the experimental groups. Study pharmacist staff, who have no direct participant contact, will oversee randomization and dispensing of study medications.

Taper Phase (4 days): Participants will undergo an open-label, step-wise buprenorphine taper. An open-label phase is necessary because buprenorphine placebo tablets/filmstrips are not available; however, this open-label design feature is of value because it increases the overall generalizability of the study results.

Post-taper Phase (4 days): Participants will continue study participation for four days (three nights) following buprenorphine discontinuation, to capture the full course of opioid withdrawal.

Study Medications: Double-blind study medication dosing will begin on the evening before Taper Day 1. Study medications will either be 20mg SUVO, 40MG SUVO, or placebo, which will be administered prior to bedtime. Though participants will be reminded to practice good sleep hygiene, no contingencies or consequences will be associated with their sleep behavior. This is because our extensive experience suggests that participants who are unable to sleep at night will attempt to sleep during the day; all sleep attempts will be captured by wrist actigraphy and nightly questionnaires and evaluated as outcome data. Placing contingencies on sleep parameters (such as no day-time sleeping) could also prompt attrition.

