Upon study completion, participants will be discharged with referral to ongoing OUD treatment and will be provided with take-home dose of intranasal naloxone (Narcan, Adept Pharmaceuticals).

Follow-up: Participants will also complete a follow-up visit approximately 5-10 days after study discharge, during which outcomes including adverse events, suicidality and depressive symptoms, need for additional OUD treatment referral, past 7-day day sleep, and illicit drug use (as assessed via self-report and a urine sample) will be collected.

Study Measures

Objective Sleep Measures:

Sleep Profiler™ Wireless EEG Monitor: The Sleep Profiler™ (Advanced Brain Monitoring, Inc.) is an unobtrusive wireless EEG device that was designed for patients to use in their home sleep environment without the assistance of a professional technician. We will train our research staff and the CRU nursing staff to assist participants with application of the device nightly so we may ensure good measurement fidelity throughout the study. The Sleep Profiler™ runs on a continuous charge for approximately 16 hours and provides three channels of frontal EEG, a pulse rate, and a sensor to detect head movement. The device is lightweight (2.5 oz) and utilizes three proprietary, pre-gelled, self-adhesive, snap electrodes. It can be comfortably applied and strapped to the forehead in 5 minutes and features a built-in impedance check to protect against poor connections, which audibly prompts the user to reaffix the electrodes when impedance is high. Participants will begin wearing the Sleep Profiler™ on Stabilization day 1, which will familiarize participants with the product before they experience withdrawal, and provide baseline data for statistical comparison. Participants will be instructed to affix the Sleep Profiler after receiving their dose of study medication and to remove it upon waking every morning.

Wrist Actigraphy: Participants will wear a triaxial accelerometer (Actigraph wGT3X-BT, Actigraph, LLC) on their non-dominant wrist for the entire duration of study enrollment. Wrist-worn actigraphy has been validated against PSG and provides an acceptable alternative measure of sleep continuity.

Self-report Sleep Measures: Additional self-report measures of sleep will be collected as part of the Primary Study Aims to corroborate quantitative analyses and increase the breadth of sleep data available. These will include measures such as:

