Routine care for sleep disturbance during opioid withdrawal includes medications such as trazodone, which are not FDA approved for sleep (but commonly used). SUVO is an ideal medication for sleep disturbance in this population. Participants currently taking benzodiazepines for sleep disturbance will not be included in this study. Study participation will be stopped if participants opt out or if study physicians determine that it is unsafe for participants to continue in the study (at any time, including in serious adverse events).

e. Justification for inclusion of a placebo or non-treatment group.

Placebo sleep medication will be utilized to rigorously assess the efficacy of SUVO in OUD patients undergoing supervised withdrawal. This is necessary for the scientific integrity of the study. Patients

experiencing persistent sleep disturbance might experience discomfort, but will not be at increased risk for serious adverse events.

f. Definition of treatment failure or participant removal criteria.

Participants will be removed from the study if they opt out or if the medical team determines it is not safe to continue in the study or if they request to discharge from the study. Additional stopping rules will include not abiding by study policies and procedures, or engaging in behaviors towards staff or other participants that are abusive. Finally, development of an intercurrent illness or condition that changes the participant's risk profile may result in a medically-related discharge from the study.

g. Description of what happens to participants receiving therapy when study ends or if a participant's participation in the study ends prematurely.

Upon study completion, participants will be discharged with referral to ongoing OUD treatment. We have relationships with several local treatment providers and participants will be referred to a treatment that best matches their recovery goals. As a safety measure, participants will complete an overdose prevention training module prior to randomization and be discharged with intranasal naloxone (Narcan).

5. Inclusion/Exclusion Criteria

Inclusion Criteria:

- Aged ≥ 18 years old
- Meets DSM-5 criteria for OUD with evidence of physical dependence on opioids.
- Provides a urine sample that tests positive for opioids.
- Seeking treatment to stop using illicit opioids.
- Willing to comply with the study protocol.

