Buprenorphine: Buprenorphine is FDA-approved for the treatment of OUD and it will be used according to that indication in this study. The buprenorphine stabilization and taper will be open label. Participants will be stabilized on buprenorphine for a maximum 3 week period before study admission, and will then complete a 3-day stabilization period (e.g., 8-16mg/day) and a 4-day step-wise taper. These approaches are standard clinical practice. This study utilized the open label taper approach in order to increase ecological validity of the supervised withdrawal paradigm.

Concomitant Medications: Consistent with standard clinical practice treatment, the following concomitant medications will be available to patients upon request: ibuprofen, acetaminophen, loperamide, milk of magnesia, and simethicone. Clonidine may be provided during the induction period only. Concomitant medications introduce a necessary confound in opioid withdrawal research because they reduce the withdrawal symptom severity that is being evaluated as part of the primary study outcomes. However, our considerable experience with opioid withdrawal studies suggests that provision of some additional supportive medications is necessary to prevent treatment attrition. Following randomization to experimental group, patients will not receive additional sleep aids or clonidine. Concomitant medication use will be PRN and compared across groups as an outcome.

- b. Justification and safety information if FDA approved drugs will be administered for non-FDA approved indications or if doses or routes of administration or participant populations are changed.

Suvorexant (SUVO): Suvorexant is approved by the FDA for the indication of insomnia at a 10mg and 20mg dose, so an IND will be requested from the FDA for the doses (20mg, 40mg) proposed in this trial. The proposed 40mg dose is being evaluated because suvorexant has a broad therapeutic window, persons with OUD might have increased orexin signaling, as evidenced by postmortem studies citing 54% more orexinergic neurons in the lateral hypothalamus of persons with OUD compared to healthy controls, and because sleep disturbance during opioid withdrawal is severe and- as of yet- no sleep-promoting pharmacotherapies have been shown to be effective in human opioid withdrawal studies.

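### The take-home naloxone kit is scheduled only at completion or discharge, so an inducted outpatient who stops attending, or a resident who leaves without a discharge contact, has no scheduled delivery

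*Combined protocol and SAP*

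**What the plan says.** **Kit.** Section 4.a, at the end of the Study Medications text, ties the kit to completion: "Upon study completion, participants will be discharged with referral to ongoing OUD treatment and will be provided with take-home dose of intranasal naloxone". Section 4.g, which also covers participation that ends early, says "participants will complete an overdose prevention training module prior to randomization and be discharged with intranasal naloxone (Narcan". Section 7.d (Early stopping rules) commits to naloxone, overdose education and a treatment referral for all patients, again on discharge.

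**Outpatient phase.** Section 4.a, Buprenorphine Induction and Stabilization: "Participants may then be maintained on buprenorphine as an outpatient for up to 3 weeks before CRU admission". During that time "participants will be required to visit the clinic on a weekly basis to exchange blister packages".

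**Training.** Section 4.a, Overdose Education: "During the stabilization period, participants will also complete a brief opioid overdose prevention computerized education session". Section 4.g sets the outer limit at randomization.

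**After discharge.** Section 4.a, Follow-up: "Participants will also complete a follow-up visit approximately 5-10 days after study discharge". The items listed for that visit include neither naloxone nor overdose education.

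**The concern.** The protocol makes a safety commitment to everyone but attaches delivery to a contact that requires the person to be present at the end. Two kinds of exit have no such contact: an inducted outpatient who misses a weekly exchange or does not come for admission and does not return, and a resident who leaves unannounced.

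The protocol foresees dropout. Section 7.c raises enrolment from 36 to 45 to allow for it, and retention is a listed outcome. Section 8.a explains that overdose risk rises once tolerance has fallen and gives completing a detoxification as an example. That rationale bears mainly on residents who leave once the taper is under way or finished. For the outpatient, who is being maintained and not tapered, no added risk from study procedures is argued. The point there is only that a promised item could be given while the person is still attending.

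**Working it through.** There is no plan figure to reproduce. The check compares the delivery points with the visit schedule.

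**1. Where the kit is scheduled**

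| Contact | Kit scheduled? | Source |
|---|---|---|
| Screening | No | 4.a Screening Visits |
| Induction day | No | 4.a Buprenorphine Induction and Stabilization |
| Weekly pack exchange | No | same |
| Admission and residential days | No | 4.a Clinical Research Unit; Overdose Education (training only) |
| Completion or discharge | Yes | 4.a, 4.g, 7.d |
| Follow-up visit | Not listed | 4.a Follow-up |

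The Abstract also mentions overdose education and naloxone, in the sentence on referral after completion, but does not clearly time the kit. Section 8.b, on minimizing risks, mentions neither.

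**2. Outpatient contacts in the longest case**

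Inputs: an outpatient period of at most 3 weeks and weekly visits (4.a). The maximum is 3 × 7 = 21 days. With induction as day 0, contacts fall on about days 0, 7, 14 and 21, the last being admission.

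| First contact missed | Last contact attended | Contacts attended with no kit scheduled |
|---|---|---|
| day 7 | day 0 | 1 |
| day 14 | day 7 | 2 |
| day 21 | day 14 | 3 |

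A shorter outpatient period gives fewer. Someone inducted on the admission day has no outpatient contacts of this kind.

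**3. When training falls**

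The word *stabilization* has two meanings. Section 4.a applies it to the weeks between screening and admission. Section 6.a applies it to a later block: participants "will then complete a 3-day stabilization period (e.g., 8-16mg/day) and a 4-day step-wise taper". With the 4 post-taper days in 4.a, that block gives 3 + 4 + 4 = 11 days, which equals the stated residential stay, so the 3 days are residential.

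The training instruction fits either meaning. A site could train at a weekly visit or wait for the residential days, and comply both ways.

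**4. What each group would miss**

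- Outpatient who stops attending: no scheduled kit, and no training if the site left it to the residential days.
- Resident who leaves without a discharge contact after randomization: no scheduled kit, but already trained under 4.g.
- Resident who leaves that way before randomization: no scheduled kit, and possibly no training yet.

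**The case against.** The strongest reply is that early exit is already handled. The completion sentence in 4.a is not the one that governs dropouts. Sections 4.g and 7.d do, and every exit route written in 4.f and 7.d is an opt-out, a request or a staff decision. That stands: a reader might infer that anyone who leaves early goes without a kit, and the documents do not support it. What remains is the person who leaves with no contact.

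Section 4.f might be thought to close even that gap, since "Additional stopping rules will include not abiding by study policies and procedures" can be read to cover a non-attender. Recording such a person as discharged does not put a kit in their hands. If they are not counted as discharged, 7.d's literal wording is not broken, and the issue is an unscheduled delivery rather than a breach.

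Three further objections stand:

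- A reader might infer that the kit is impossible to supply before discharge. Nothing bars staff from giving one earlier. The plan simply does not schedule it.
- A reader might infer that outpatients go untrained. Because 4.a uses *stabilization* for the outpatient weeks, training may already take place then. This is an ambiguity, not a demonstrated omission.
- A reader might count the taper and post-taper days on the unit as days of unmet need. Section 8.a does not say that tolerance is lost from the first taper day, and a take-home kit is not what protects someone who is still resident.

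**Conclusion.** The point holds in a limited form. The plan schedules the kit only at completion or discharge, so two kinds of unannounced exit have no scheduled delivery, although 7.d's commitment covers all patients. Whether training precedes admission cannot be determined from the text.

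In the longest outpatient case the size is 1 to 3 attended contacts with no kit scheduled. This assumes the full 3 weeks and exactly weekly visits. The documents give no count of people who would leave without a discharge contact, and none is estimated here. They also do not show that those who drop out usually miss the discharge contact.

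This is a low-cost participant-safety improvement to consider. It does not affect sample size, power or the analysis.

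**What to change.** In 4.a, 4.g and 7.d, state that the naloxone kit is given and the overdose module completed no later than the dispensing of the first take-home buprenorphine pack. For those inducted on the admission day, require both before randomization. At discharge, check that the participant still has the kit and replace it if not. This wording also removes the ambiguity about when training falls.

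**Cost.** Protocol wording in three sections, a few additional or replacement kits, and a short module to fit in at screening or on a busy induction day. For people who reach discharge, the kit and module are moved earlier, not added.

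**Limits.** A resident who leaves unannounced benefits only if the kit goes with them. Someone inducted at admission who leaves before randomization could still be missed unless both items are given on arrival.

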This study is designed as a dose-finding study of SUVO compared to placebo. Briefly, OUD patients seeking supervised withdrawal will be admitted into a clinical research unit and stabilized onto buprenorphine before being randomly assigned to study condition. All participants will then undergo a routine buprenorphine taper, followed by a post-taper phase. Participants will be randomized to receive either placebo, SUVO 20mg, or SUVO 40mg and we hypothesize that one or both doses of SUVO will improve total sleep time relative to placebo. The dose of SUVO identified as most efficacious in this study will be used in a subsequent study. This study is supported by power analyses that were conducted for both Aims 1 and 2. Primary outcomes of this study include total sleep time as measured via an ambulatory electroencephalography (EEG) device, wrist actigraphy, and self-reported sleep as well as abuse liability measures of SUVO. Participants will be referred to ongoing treatment following completion of the study and will be provided with opioid overdose education and Narcan as an additional prevention measure.

2. Objectives (include all primary and secondary objectives)

- **Primary Aim 1: Evaluate whether 20mg and 40mg suvorexant, relative to placebo, improves total sleep time among patients undergoing routine opioid withdrawal, assessed via (a) EEG, (b) actigraphy, and (c) self-report.**

- Primary Aim 2: Evaluate the abuse liability of 20mg SUVO versus 40mg SUVO relative to placebo using self-report ratings, and secondary measures that include a hypothetical purchase task and drug ratings.
 - Secondary Aim 1: Evaluate whether 20mg SUVO and 40mg SUVO decreases self-reported measures of drug effects and craving, opioid withdrawal, concomitant medication use, and self-reported stress; decreased diurnal salivary cortisol and serum cortisol/adrenocorticotropic releasing hormone; and improves treatment retention relative to placebo.
3. **Background** (briefly describe pre-clinical and clinical data, current experience with procedures, drug or device, and any other relevant information to justify the research)

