Stress and Craving Measures: Several brief and validated measures (such as those below) will be used to inform potential mechanism underlying effects and whether prospective studies to examine these effects more thoroughly are warranted.

1. *Visual Analog Ratings*: Self-report ratings of opioid craving (e.g. How much do you want to use right now? How much do you want to avoid using right now? How much control would you have over using if someone offered you opioids right now?) and stress (e.g. How stressed do you feel right now? How much is opioid withdrawal contributing to your stress?)
2. *Diurnal Cortisol*: Salivary cortisol will be collected several times daily. Diurnal cortisol is a measure of HPA-axis function that affects the sleep-wake cycle (Edwards, Evans, Hucklebridge, & Clow, 2001) .
3. *Additional HPA-axis Measures*: One blood sample will be taken during the stabilization, withdrawal, and post-withdrawal periods to measure change in adrenocorticotrophic hormone to cortisol ratios. These measures have been associated with treatment outcomes in other substance using populations including cocaine use disorder (Sinha, Garcia, Paliwal, Kreek, & Rounsaville, 2006) .

b. Study duration and number of study visits required of research participants.

The entire study will consist of one screening visit and a residential stay over the course of 11 days and 10 nights. All study activities will take place at the BPRU and the Bayview CRU.

c. Blinding, including justification for blinding or not blinding the trial, if applicable.

The only blinded medication in this study is SUVO. Since this is the medication of interest, participants will be blinded to ensure study rigor and assess the utility of SUVO to treat sleep disturbance compared to placebo. The buprenorphine taper and concomitant medications will not be blinded in order to mimic the real-world experience of supervised opioid withdrawal and increase ecological validity.

d. Justification of why participants will not receive routine care or will have current therapy stopped.

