The first primary outcome for this study will be total sleep time during opioid withdrawal as determined by EEG, and supplemented by actigraphy and self-report.

The second primary outcome for this study is abuse liability, which will be assessed via next day measures of Drug Liking measured on a 0-100 point VAS.

b. Secondary outcome variables.

(1) Secondary outcomes from the Sleep Profiler EEG will include measures of sleep continuity and architecture

(2) Secondary actigraphy outcomes will include sleep and activity-related outcomes

(3) Secondary self-report sleep ratings will include self-reported sleep measures

(4) Opioid withdrawal severity, assessed via the subjective opiate withdrawal scale.

(5) Other secondary outcomes include a hypothetical purchasing task, other self-report VAS measures of abuse liability (e.g. drug effect, good effect, bad effect, perceived drug value), self-reported measures of drug craving, VAS opioid withdrawal, stress; diurnal cortisol; vital signs; and retention in treatment.

c. Statistical plan including sample size justification and interim data analysis.

Power Analyses: In order to support the planned 2 and 3 group analyses (comparing 20mg SUVO, 40mg SUVO, and placebo), we used G-power to derive sample sizes from previously reported effect sizes in clinical trials on SUVO and hypothetical opioid purchase task data; both displayed large effect sizes (≥ 0.70). A total sample size of 36 participants (12 per group) would provide 95% power to detect an effect size of 0.70 for difference in total sleep time (Primary Aim 1) and difference in the opioid demand curve (Secondary Aim 1). A study on the abuse liability of SUVO, zolpidem, and placebo in non-ODU patients (Schoedel et al., 2016) reported a medium to large effect size on drug liking (0.45), suggesting a total sample size of 34 would provide 90% power to detect an effect size of 0.45 for Primary Aim 2. To protect against participant drop out, we are proposing to enroll 15 participants per medication group (total N=45).

Analyses: All Primary Outcomes (total sleep time, opioid withdrawal severity, and abuse liability) will be compared as a function of group (20mg SUVO, 40mg SUVO, and placebo; or SUVO [collapsed] vs placebo) and phase (taper vs. post-taper), as well as group by day (7 nights) using 2-factor Proc Mixed analyses with Tukey posthoc testing. Both peak values and Area-under-the-curve (AUC) values of total sleep time, SOWS scores, and Drug Liking

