Secondary measures will be additional ratings on the hypothetical purchase task, SOWS and VAS ratings of opioid withdrawal, VAS ratings of abuse liability, self-reported craving, self-reported stress, perceived drug value, and diurnal salivary cortisol (measured via AUC values and mean daily cortisol) and cortisol/ACTH ratios. Purchase task data will be fit to opioid demand curves for comparison. **Analyses:** All outcomes will be compared as a function of group (20mg SUVO, 40mg SUVO, and placebo) and phase (taper vs. post-taper), as well as group by day (7 nights) using area-under-the-curve (AUC). The taper and post-taper periods will then be derived and compared as a function of group and group x phase using independent groups t-tests and ANOVAs with Tukey post-hoc for pairwise comparisons. If data does not meet ANOVA assumptions, mixed model regressions will be used. Exploratory analyses will include linear and multivariate regression models to examine the relationship between measures of sleep, stress, opioid withdrawal, and craving. Logistic regression will be used to examine the relationship between sleep, stress, opioid withdrawal, and craving on the likelihood of treatment attrition.

d. Early stopping rules.

Patients will discontinue their study participation if they request to be discharged, have a serious adverse event, or if the study physicians decide it is in the patient's best interest to be removed from the study. All patients will be discharged with naloxone, opioid overdose education, and referral to outpatient OUD treatment.

8. Risks

a. Medical risks, listing all procedures, their major and minor risks and expected frequency.

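### The HPA blood outcome is ACTH to cortisol in section 4.a and cortisol/ACTH in section 7.c; tests on the two raw ratios can differ, and the stabilization sample is not used

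*Combined protocol and SAP*

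**What the plan says.** The combined protocol and SAP describes the HPA blood measure in three places.

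- **Section 2, Secondary Aim 1** predicts "decreased diurnal salivary cortisol and serum cortisol/adrenocorticotropic releasing hormone". It gives a direction (a decrease) but does not use the word ratio.
- **Section 4.a, Stress and Craving Measures, Additional HPA-axis Measures** sets the sampling: "One blood sample will be taken during the stabilization, withdrawal, and post-withdrawal periods". The stated purpose is "to measure change in adrenocorticotrophic hormone to cortisol ratios". No direction is given.
- **Section 7.c, secondary measures** lists "diurnal salivary cortisol (measured via AUC values and mean daily cortisol) and cortisol/ACTH ratios" for analysis, again with no direction.

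For these outcomes 7.c compares groups by phase, taper against post-taper, and by day over seven nights using AUC. The tests are "independent groups t-tests and ANOVAs with Tukey post-hoc for pairwise comparisons". The fallback is: "If data does not meet ANOVA assumptions, mixed model regressions will be used". No transformation is stated for either.

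**The concern.** Sections 4.a and 7.c name reciprocal quantities and nothing explains the switch. Two things follow.

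First, the sign of the hypothesis for the analysed variable is not fixed until someone decides what the slash in the aim means and which hormone is the numerator.

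Second, it is easy to suppose that inverting a ratio only flips the sign of a two-sided test. That is true of the log ratio but not of the raw ratio, so the p-value can also depend on the orientation.

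Separately, 4.a says the samples are for measuring change and takes one during stabilization, but the 7.c contrast starts at the taper.

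At stake is how a named part of Secondary Aim 1 is read. As written, the numerator, the scale and the use of baseline could all be settled after the data are seen.

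**Working it through.** **1. The passages side by side**

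| Place | Quantity | Called a ratio? | Direction |
|---|---|---|---|
| Secondary Aim 1 | cortisol / ACTH-type hormone | no | decrease |
| 4.a | ACTH to cortisol | yes | none |
| 7.c | cortisol / ACTH | yes | none |

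Write R = cortisol/ACTH, so that the 4.a measure is 1/R. If the aim means R, its predicted decrease is an increase in 1/R. If the aim means that serum cortisol and the other hormone each fall, neither R nor 1/R has a predicted direction, because R can rise, fall or stay the same when both parts fall.

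**2. Why the raw tests differ**

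The t statistic is (difference in means) / (its standard error). The mean of 1/R is not 1/(mean of R). High values of R dominate the mean and SD of R, and low values dominate those of 1/R. The two statistics are therefore not mirror images. On the log scale log(1/R) = -log R, so the statistic changes sign and the p-value is identical.

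**3. Inputs for the size of the effect**

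The documents give no SD, expected effect, alpha or power for this outcome, so there is no figure to reproduce. The group sizes come from the power paragraph of 7.c: "A total sample size of 36 participants (12 per group) would provide 95% power to detect an effect size of 0.70", with 15 per group enrolled. As a check on that sentence, a one-way ANOVA with three groups, N=36, f=0.70 and alpha 0.05 has noncentrality 36 × 0.70² = 17.64 and power 95.7%. This agrees with the stated 95% but has no bearing on the HPA ratio.

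Everything else is assumed: lognormal R, the same log SD in both arms (0.2 to 0.8), a true shift of 0, 0.5 or 1 log SD, and two-sided alpha 0.05.

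**4. Two-arm simulation** (40,000 trials per setting, Monte Carlo standard error about 0.2 points or less)

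Percentage of trials in which exactly one of the t-tests on R and 1/R has p<0.05, for n=12 / n=15 per arm:

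| Log SD | No effect | 0.5 SD shift | 1 SD shift |
|---|---|---|---|
| 0.2 | 1.6 / 1.8 | 5.0 / 5.6 | 6.5 / 6.2 |
| 0.3 | 2.5 / 2.7 | 6.7 / 8.3 | 9.8 / 9.2 |
| 0.5 | 3.5 / 4.0 | 10.7 / 12.3 | 17.1 / 15.9 |
| 0.8 | 4.8 / 5.1 | 13.9 / 17.1 | 26.1 / 26.3 |

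The ranges are about 2-5%, 5-17% and 6-26%. On the log scale the disagreement is 0% throughout.

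**5. Three-arm check** (20,000 trials per setting)

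This used the same log SDs, a high-dose shift of 0, 0.7 or 1.4 log SD with half that at the low dose, and an assumed baseline correlation of 0.5. ANOVAs on R and 1/R disagreed in 1.8% to 29.5% of trials for post-baseline levels and in 2.9% to 49.7% for raw change from baseline. The upper ends belong to the largest spreads. With log SD of 0.3 or less the ranges were 2-11% for levels and 3-21% for change.

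**6. Use of the stabilization sample**

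The three samples fall in stabilization, withdrawal and post-withdrawal. The phase contrast in 7.c has two levels, taper and post-taper. The stabilization value is in neither, so no stated analysis estimates or adjusts for change from it. One blood sample per period also cannot supply an AUC over seven nights, so the generic wording of 7.c does not fit this measure.

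**The case against.** The strongest reply has four parts.

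- **The analysis section does name one orientation.** Section 7.c says cortisol/ACTH, and the aim uses the same order. The sentence that differs describes sample collection. If the orientation is reported, a reader can invert it. This stands in part: it makes 7.c the more likely intention, but it does not settle the scale or what the aim's slash means.
- **A reader might infer that the predicted decrease is reversed between sections.** The documents do not support that as fact. The aim never says ratio, and 4.a and 7.c predict no direction. The reversal holds only if the aim means the ratio.
- **A reader might infer that the two tests often conflict.** The documents give no variability from which to say so. With small spread or no effect the rate is a few per cent, and a log analysis, which the plan neither requires nor excludes, would make it zero. Nor do significant results point opposite ways. With no effect and log SD of 0.3 to 0.8, the raw means of R and 1/R are both higher in the same arm in 12% to 30% of trials, but those differences are noise. At a 1 SD shift the share is 2.5% or less, and in no simulated trial were both t-tests significant with the same sign. The disagreement is between significant and not significant.
- **Comparing randomised groups after baseline is valid without a baseline value.** This stands. Leaving out the stabilization sample causes no bias. It means that the stated purpose, change, is not addressed and that available precision is not used.

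The consequence is also limited. Section 4.a presents these measures as informing mechanism and the case for later studies. The list in 7.b names diurnal cortisol but not the blood ratio, and no sample size rests on it.

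**Conclusion.** The inconsistency is real: 4.a and 7.c name reciprocal outcomes, and the aim is ambiguous between a ratio and two levels. With the t-tests and ANOVAs as written, on an unstated scale, the choice of orientation can change whether p<0.05. In two-arm comparisons of 12 to 15 per arm the rate is about 2-5% with no effect, 5-17% at a 0.5 SD shift and 6-26% at 1 SD. These rates rest on an assumed lognormal ratio with log SD of 0.2 to 0.8 and should be read as a range of possibilities, not as an estimate for this trial. The stabilization sample, taken to measure change, has no place in the stated comparison.

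This is a minor-to-moderate correction to a mechanistic secondary measure. No primary conclusion and no sample size depends on it.

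**What to change.** Use one definition in Secondary Aim 1, section 4.a and section 7.c: log(cortisol) minus log(ACTH), with the hypothesised direction stated and the same hormone name throughout. If the aim was meant to concern the two hormone levels separately, say so, give a direction for each, and label the ratio as a further measure without a directional hypothesis.

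In 7.c, give this outcome its own sentence in place of the AUC wording. Compare groups on the taper and post-taper log ratios, with the stabilization log ratio as covariate. Confirm that the stabilization sample is drawn before the first blinded dose, which is given on the evening before Taper Day 1. Report group differences back-transformed as ratios with 95% confidence intervals.

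On the log scale either orientation gives the same test with the opposite sign, so the conflict disappears. The covariate also helps precision: at an assumed baseline correlation of 0.5, the residual variance is 1 - 0.5² = 0.75 of that for the unadjusted value. Naming one orientation everywhere, without the log, would be the minimum repair. It would remove the contradiction but leave a skewed raw ratio under t-tests.

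The cost is protocol and SAP wording only, best settled before unblinding. No new samples or data are needed.
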